4 SELECTION OF SUBJECTS

4.1 INCLUSION CRITERIA

Each subject must meet all of the following criteria to be enrolled in the study:

- 1. Women aged 18 years and above;
- 2. Confirmed cervical infection with HPV types 16 and/or 18 at screening by $cobas^{TM}$ HPV test;
- 3. Cervical tissue specimen/slides provided to Study Pathology Adjudication Committee for diagnosis must be collected within 10 weeks prior to anticipated date of first dose of study drug;
- 4. Histologic evidence of cervical HSIL as confirmed by PAC at screening;

- 5. Must understand, agree and be able to comply with the requirements of the protocol. Subjects must be willing and able to provide voluntary consent to participate and sign a Consent Form prior to study-related activities;
- 6. Must be judged by Investigator to be an appropriate candidate for the protocol-specified procedure (i.e. excision, 4-quadrant biopsy with ECC, or 4-quadrant biopsy) required at Week 36;
- 7. Satisfactory colposcopy at screening, defined as full visualization of the squamo-columnar junction (Type I or II transformation zone) and complete visualization of the upper limit of aceto-white epithelium or suspected CIN disease;
- 8. Cervical lesion that is accessible for sampling by biopsy instrument (e.g. Mini-Tischler device);
- 9. Cervical lesion of adequate size to ensure that a visible lesion remains after screening biopsy;
- 10. Must meet one of the following criteria with respect to their reproductive capacity:
 - a) Is post-menopausal as defined by spontaneous amenorrhea for more than 12 months or spontaneous amenorrhea for 6-12 months with FSH level >40 mIU/mL
 - b) Is surgically sterile due to absence of ovaries or due to a bilateral tubal ligation/occlusion performed more than 12 months prior to screening
 - c) WOCBP is willing to use a contraceptive method with failure rate of less than 1% per year when used consistently and correctly from screening until Week 36. The following methods are acceptable:
 - Hormonal contraception: either combined or progestin-alone including oral contraceptives, injectable, implants, vaginal ring, or percutaneous patches. Hormonal contraceptives must not be used in subjects with a history of hypercoagulability (e.g., deep vein thrombosis, pulmonary embolism).
 - O Abstinence from penile-vaginal intercourse when this is the subject's preferred and usual lifestyle
 - o Intrauterine device or intrauterine system
 - o Male partner sterilization at least 6 months prior to the female subject's entry into the study, and this male is the sole partner for that subject
- 11. Normal screening ECG or screening ECG with no clinically significant findings, as judged by the investigator.

4.2 EXCLUSION CRITERIA

Subjects meeting any of the following criteria will be excluded from enrollment in the study:

1. Microscopic or gross evidence of adenocarcinoma-in-situ (AIS), high grade vulvar, vaginal (inclusive of cervical HPV-related lesions that extend into the vaginal vault), or anal intraepithelial neoplasia or invasive cancer in any histopathologic specimen at screening;

- 2. Cervical lesion(s) that cannot be fully visualized on colposcopy due to extension high into cervical canal at screening;
- 3. History of ECC which showed cervical HSIL indeterminate, or insufficient for diagnosis (ECC is not performed as part of study screening);
- 4. Treatment for cervical HSIL within 4 weeks prior to screening;
- 5. Pregnant, breastfeeding or considering becoming pregnant during the study;
- 6. History of previous therapeutic HPV vaccination (licensed prophylactic HPV vaccines are allowed, e.g. Gardasil[™], Cervarix [™]);
- 7. Presence of any abnormal clinical screening laboratory values greater than Grade 1 per Common Toxicity Criteria for Adverse Events (CTCAE) v 4.03 or less than Grade 1 but deemed clinically significant by the investigator within 30 days prior to Day 0;
- 8. Immunosuppression as a result of underlying illness or treatment including:
 - a) History of or positive serologic test for HIV at screening (performed within 30 days prior to Day 0)
 - b) Primary immunodeficiencies
 - c) Long term use (≥ 7 days) of oral or parenteral glucocorticoids at a dose of ≥20 mg/day of prednisone equivalent; (use of inhaled, otic, and ophthalmic corticosteroids are allowed)
 - d) Current or anticipated use of disease modifying doses of anti-rheumatic drugs (e.g., azathioprine, cyclophosphamide, cyclosporine, methotrexate), and biologic disease modifying drugs such as TNF-α inhibitors (e.g. infliximab, adalimumab or etanercept)
 - e) History of solid organ or bone marrow transplantation
 - f) Any prior history of other clinically significant immunosuppressive or clinically diagnosed autoimmune disease that may jeopardize the safety of the subject or require therapy that would interfere with study assessments or endpoint evaluation, or otherwise impact the validity of the study results.
- 9. Receipt of any non-study, non-live vaccine within 2 weeks of Day 0;
- 10. Receipt of any non-study, live vaccine (e.g. measles vaccine) within 4 weeks of Day 0;
- 11. Current or history of clinically significant, medically unstable disease which, in the judgment of the investigator, would jeopardize the safety of the subject, interfere with study assessments or endpoint evaluation, or otherwise impact the validity of the study results (e.g. chronic renal failure; angina, myocardial ischemia or infarction, class 3 or higher congestive heart failure, cardiomyopathy, or clinically significant arrhythmias);
- 12. Malignancy or treatment for malignancy within 2 years of screening, with the exception of superficial skin cancers that only require local excision;
- 13. Presence of acute or chronic bleeding or clotting disorder that would contraindicate IM injections, or use of blood thinners (e.g. anticoagulants or antiplatelet drugs) within 2 weeks of Day 0;

- 14. History of seizures unless seizure free for 5 years with the use of one or fewer antiepileptic agents;
- 15. Sustained, manually confirmed, sitting systolic blood pressure >150 mm Hg or <90 mm Hg or a diastolic blood pressure >95 mm Hg at Screening or Day 0;
- 16. Resting heart rate <50 bpm (unless attributable to athletic conditioning) or >100 bpm at screening or Day 0;
- 17. Prior major surgery within 4 weeks of Day 0;
- 18. Participation in an interventional study with an investigational compound or device within 30 days of signing informed consent; participation in an observational study is permitted;
- 19. Less than two acceptable sites available for IM injection considering the deltoid and anterolateral quadriceps muscles;
- 20. Tattoos, keloids or hypertrophic scars located within 2 cm of intended treatment site;
- 21. Cardioverter-defibrillator or pacemaker (to prevent a life-threatening arrhythmia) that is located in ipsilateral deltoid injection site (unless deemed acceptable by a cardiologist);
- 22. Metal implants or implantable medical device within the electroporation area;
- 23. Active drug or alcohol use or dependence that, in the opinion of the investigator, would interfere with adherence to study requirements;
- 24. Prisoner or subject who is compulsorily detained (involuntarily incarcerated) for treatment of either a psychiatric or physical (i.e. infectious disease) illness;
- 25. Active military service personnel;
- 26. Study-related staff or family member of study-related staff;
- 27. Any illness or condition that in the opinion of the investigator may affect the safety of the subject or the evaluation of any study endpoint.

4.3 DISCONTINUATION/WITHDRAWAL OF STUDY SUBJECTS

4.3.1 CRITERIA FOR DISCONTINUATION OF INVESTIGATIONAL PRODUCT

Subjects who manifest Grade 4 toxicity attributable to the study treatment will be discontinued from the study treatment. Subjects will not receive further study treatment but will be encouraged to continue follow-up safety assessment through study discharge and not discontinue from the study.

If a subject manifests Grade 3 toxicity attributable to the study treatment, the medical monitor and Investigator will discuss whether further treatment should be continued for that subject.

4.3.2 CRITERIA FOR WITHDRAWAL FROM THE STUDY

All randomized subjects should be encouraged to complete all study treatments and follow-up visits. A subject will be considered to have completed the study when she completes all scheduled study treatments and follow-up visits. However, a subject may voluntarily withdraw from study participation at any time or be withdrawn at any time at the discretion of the investigator for any maternal obstetrical or medical complications after consultation with the medical monitor.

Should a subject fail to attend the clinic for a required study visit, the site should attempt to contact the subject and reschedule the missed visit as soon as possible. The site should also counsel the subject on the importance of maintaining the assigned visit schedule for follow-up and treatment of HSIL (CIN2, CIN3), and ascertain whether or not the subject wishes to and/or should continue in the study based on previous noncompliance. In cases where the subject does not return for the rescheduled visit or cannot be reached to reschedule the missed visit, the site should make every effort to regain contact with the subject (3 telephone calls and if that fails, then a certified letter to the subject's last known mailing address) so that the subject's disposition can be considered as withdrawn from the study (i.e. lost to follow-up). If the contact with subject is re-established, site should contact medical monitor to discuss whether subject can continue study treatment or follow-up visits for the study. For all other subjects withdrawing from the study, an alternative reason for discontinuation should be recorded in the eCRF.

4.3.3 SPONSOR NOTIFICATION OF DISCONTINUATION/ WITHDRAWAL

The investigator or study coordinator must notify the Sponsor within 24 hours if a subject has been discontinued/withdrawn due to an AE. If a subject discontinues from the study or is withdrawn from the study prior to study completion, all applicable activities scheduled for the final study visit should be performed at the time of discontinuation. The investigator will make every effort to have all scheduled immune assessment blood samples collected as indicated in the Schedule of Events in the synopsis, Table 1. Any AEs and/or SAEs present at the time of discontinuation/withdrawal should be followed in accordance with the safety requirements outlined in section 7.1 – Safety Parameters.

4.3.4 REASON FOR DISCONTINUATION/WITHDRAWAL

The primary reason for a subject discontinuing further dosing or withdrawal from the study itself is to be selected from the following standard categories and recorded on the CRF:

- Adverse Event (Adverse Reaction): Clinical or laboratory events occurred that, in the medical judgment of the investigator for the best interest of the subject, are grounds for discontinuation. This includes serious and non-serious adverse events regardless of relation to study drug.
- Death of subject
- Subject voluntarily withdrew consent: The subject desired to withdraw from further participation in the study in the absence of an investigator-determined medical need to withdraw. If the subject gave a reason for withdrawal, it must be recorded on the CRF. This reason does not allow for further data collection and should not be selected if follow-up data collection of this subject is anticipated by the subject.
- Investigator decision to withdraw the subject from participation: Investigator determined a medical need to withdraw the subject. Investigator must consult the Sponsor's Medical Monitor before withdrawing a subject from participation in the study
- Protocol Violation: The subject's findings or conduct failed to meet the protocol entry criteria or failed to adhere to the protocol requirements (e.g., treatment noncompliance, failure to return for defined number of visits). The violation should be discussed with the Sponsor's Medical Monitor prior to discontinuation of study treatments or study withdrawal.
- Lost to Follow-up: The subject fails to attend study visits and study personnel are unable to contact the subject after repeated attempts including telephone calls, letter sent by certified mail or equivalent.
- Other: The subject was terminated for a reason other than those listed above, such as the termination of the study by the Sponsor.

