The information in this document is considered privileged and confidential by Inovio Pharmaceuticals and may not be disclosed to others except to the extent necessary to obtain Institutional Review Board/Ethics committee approval and informed consent, or as required by local regulatory authorities. Persons to whom this information is disclosed must be informed that this information is privileged and confidential and that it should not be further disclosed without the written permission of Inovio Pharmaceuticals. Any supplemental information added to this document is also confidential and proprietary information of Inovio Pharmaceuticals and must be kept in confidence in the same manner as the contents of this document.

SUMMARY OF CHANGES

The following is a list of significant protocol changes from HPV-301 protocol version 2.1 dated 10 June 2016 to HPV-301 protocol version 3.0 dated 23 September 2016. All other changes are administrative and do not significantly affect the safety of subjects, study scope, or scientific quality of the protocol.

- 1. Name of the investigational product has been changed from VGX-3100X to VGX-3100. The term VGX-3100 as used in this document denotes 3.0 ± 0.2 mg/mL pGX3001 bulk plasmid and 3.0 ± 0.2 mg/mL pGX3002 bulk plasmid in saline sodium citrate (SSC) buffer, refrigerated formulation
- 2. The primary analysis for the study has been changed from modified-intention-to-treat (mITT) based on complete data to intention-to-treat (ITT) analysis. Based on this change, the number of subjects to be enrolled in the study is now 198 instead of 165
- 3. The following modification have been made to the objectives and endpoints:
 - a. Changed the exploratory objective of "clearance of HPV-16 and/or HPV-18 infection from anatomic location outside the cervix" to secondary objective
 - b. Added association of microRNA profile to the exploratory objective
 - c. Specified the countries where patient reported outcome will be collected in the exploratory endpoint
- 4. The following modification have been made to inclusion and exclusion criteria:
 - a. Inclusion criteria 10c) clarified the duration of use of contraceptive method from screening until week 36
 - b. Exclusion criteria 4 has been modified to remove the treatment of genital warts within 4 weeks of screening
- 5. The following modification have been made to the study evaluation:

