PBMC Peripheral Blood Mononuclear Cells

PDC Participant Diary Card PRO Patient Reported Outcomes

PE Physical exam

PHI Protected Health Information

PI Principal Investigator

PP Per Protocol

SAE Serious Adverse Event
SID Subject Identification
SOC System Organ Class
SSC Saline Sodium Citrate
sWFI Sterile Water for Injection

TNF Tumor Necrosis Factor ULN Upper Limit of Normal

WOCBP Women of Childbearing Potential

II CLINICAL PROTOCOL SYNOPSIS

Title of Study: A Prospective, Randomized, Double-blind, Placebo-Controlled Phase 3 Study of VGX-3100 Delivered Intramuscularly followed by Electroporation with CELLECTRA[™] 5PSP for the Treatment of HPV-16 and/or HPV-18 related High Grade Squamous Intraepithelial Lesion (HSIL).¹ of the Cervix

Estimated Number of Study Centers and Countries/Regions: Approximately 125 Sites in up to 25 Countries

Study Phase: 3

Primary Hypothesis: Three 6 mg doses of VGX-3100 (DNA Plasmids encoding E6 and E7 proteins of HPV-16 and HPV-18) delivered intramuscularly (IM) followed by electroporation (EP) with CELLECTRA[™] 5PSP to adult women with histologically confirmed HSIL[Cervical Intraepithelial Neoplasia (CIN)2, CIN3] of the cervix, associated with HPV-16 and/or HPV-18 will result in a higher percentage of women with histopathological regression of cervical HSIL lesions to no evidence of cervical HSIL and virologic clearance of HPV-16 and/or HPV-18 compared to placebo delivered IM followed by EP with CELLECTRA[™] 5PSP at the Week 36 visit

Study Drug Dose 6 mg (1 ml)	
Administration	Intramuscular injection followed by EP with the CELLECTRA™ 5PSP device
Schedule Day 0, Week 4, and Week 12 study visits	
No. of Subjects Approximately 198 subjects will be randomized in a 2:1 ratio to recover VGX-3100 or placebo	
Study Duration 88 weeks	
Primary Objective	Determine the efficacy of VGX-3100 compared with placebo with respect to combined histopathologic regression of cervical HSIL and virologic clearance of HPV-16 and/or HPV-18
Primary Endpoint	Proportion of subjects with no evidence of cervical HSIL on histology (i.e. biopsy or excisional treatment) and no evidence of HPV-16 and/or HPV-18 in cervical samples by type specific HPV testing at Week 36 visit

¹ Terminology based on 2012 consensus recommendation on Lower Anogenital Squamous Terminology (LAST) from the American Society of Colposcopy and Cervical Pathology (ASCCP) and the College of American Pathologists (CAP)

Secondary Objectives	Associated Secondary Endpoints

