2 STUDY DESIGN

This Phase 3 study design is based upon the Phase 2b study design and results. HPV-301 is a prospective, randomized, double-blind, placebo controlled study to determine the efficacy, safety, and tolerability of VGX-3100 administered by IM injection followed by EP delivered with CELLECTRA[™] 5PSP in adult women with histologically confirmed cervical HSIL (CIN2, CIN3) associated with HPV-16/18.

A sample of approximately 198 subjects will be randomized to receive either 6 mg (in 1 ml) VGX-3100 or placebo, each IM followed by EP, in a 2:1 ratio. This sample size provides 90% power to declare VGX-3100 superior to placebo, assuming, based upon Phase 2b study results, that the true proportion of subjects whose lesion(s) regress and whose HPV-16/18 clears is 35% and 14% for VGX-3100 and placebo, respectively.

Subjects will be randomized in a stratified manner according to (a) the CIN severity observed in the biopsy specimens at screening (i.e. CIN2 vs. CIN3), (b) BMI category (≤25 vs. >25 kg/m²), and (c) age category (<25 years vs. ≥25 years). To ensure CIN2 disease is not over-represented in the study, the percentage of subjects enrolled with CIN2 will not exceed 50% of the total enrolled.

To be eligible for the study, subjects age 18 years and above must consent to participate and have cervical biopsy/biopsies of the cervical lesion(s) at the time of screening. Slides of the biopsy will be sent to a PAC in a blinded manner to establish the presence of cervical HSIL within screening. In order to be eligible for continued enrollment, the PAC must assign the histologic diagnosis of cervical HSIL. Subjects must also have a cervical specimen test positive for HPV-16/18 by cobas[™] HPV test to be eligible for participation in the study.

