2.1.3 DEFINITION OF RESPONDER AND NON-RESPONDER

Responder and non-responder definitions (Table 7) for the primary endpoint takes into account both histopathologic regression of cervical HSIL and virologic (HPV-16 and/or HPV-18) clearance from cervical samples since HPV persistence is an important factor in the clinical progression of HSIL. The responder definition also excludes subjects whose cervix is biopsied at any time after their initial biopsy to determine eligibility and the Week 36 endpoint tissue collection. This exclusion is included to reduce the potential for artefactual increases in the treatment effect caused by removal of HSIL tissue and potentially HPV-16/-18 by unplanned interval biopsies. To qualify as a responder, the subject must have: 1) an acceptable histology specimen at Week 36, which is interpretable by the independent PAC, and 2) an acceptable HPV ThinPrepTM sample at Week 36, with an associated valid HPV-testing result. A responder is defined as a subject with: 1) no histologic evidence of cervical HSIL and 2) no evidence of HPV-16 or HPV-18 at the Week 36 evaluation. Also, to be considered a responder, the subject must not have had an unscheduled cervical tissue sample obtained after study entry and the Week 36 visit. Conversely, any subject with: 1) histologic evidence of cervical HSIL at the Week 36 evaluation, OR 2) evidence of HPV-16 or HPV-18 at the Week 36 visit, OR 3) a cervical tissue sample obtained after study entry and the Week 36 visit OR 4) no Week 36 visit sample will be designated as a non-responder.

Table 7. Definition of Primary Endpoint Responder and Non-Responder

Responder	Non-Responder
	Subject with histologic evidence of cervical HSIL, AIS, cervical carcinoma at Week 36 evaluation
Subject with no histologic evidence of cervical	OR
HSIL ^a at Week 36 evaluation and no evidence of HPV-16 and/or HPV-18 at Week 36 ^b	Subject with evidence of HPV-16 or HPV-18 at Week 36
AND	OR
Subject in which a cervical tissue sample was NOT obtained between collection of tissue to determine entry eligibility up to Week 36 primary endpoint visit	Subject in which an additional cervical tissue sample was obtained between collection of tissue to determine entry eligibility up to Week 36 primary endpoint visit
	OR
	Subject with no Week 36 primary endpoint sample result

^a no evidence of HSIL is defined by histology as negative, squamous atypia, or LSIL

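### Version 3.0 scores a missing Week 36 sample as non-response, yet its withdrawal rules still let sites take willing women out of the study for non-compliance, missed visits or unmet entry criteria

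*Protocol*

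**What the plan says.** The analysis side changed in version 3.0. Item 2 of the Summary of Changes states: "The primary analysis for the study has been changed from modified-intention-to-treat (mITT) based on complete data to intention-to-treat (ITT) analysis". Section 2.1.3 and Table 7 add a fourth non-responder category, "Subject with no Week 36 primary endpoint sample result", and item 14 of the Summary says that missing data count as failure in the ITT efficacy analysis.

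The conduct side, in Section 4.3 of version 3.0, reads as follows.

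- **4.3.2.** After a missed visit, the site is to "ascertain whether or not the subject wishes to and/or should continue in the study based on previous noncompliance". If contact with a lost woman is regained, whether she may have further doses or even follow-up visits is a matter for discussion with the medical monitor. She may also "be withdrawn at any time at the discretion of the investigator for any maternal obstetrical or medical complications after consultation with the medical monitor".
- **4.3.4.** One list of reasons serves both stopping doses and leaving the study. Its protocol-violation entry covers unmet entry criteria and the case where the woman's conduct "failed to adhere to the protocol requirements (e.g., treatment noncompliance, failure to return for defined number of visits". The entry closes by naming study withdrawal as one possible result, after discussion with the sponsor's medical monitor.
- **4.3.3.** At withdrawal, the final-visit activities are performed. In the Schedule of Events, the Week 88 visit has ThinPrep and colposcopy but no biopsy or excision.
- **4.3.1.** Women stopped for attributable Grade 4 toxicity "will be encouraged to continue follow-up safety assessment through study discharge and not discontinue from the study".

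**The concern.** Under a complete-data analysis, a woman withdrawn by the site drops out of the comparison. Under the version 3.0 rule she stays in the denominator as a treatment failure. The withdrawal text in 4.3.2 and 4.3.4 was not adjusted to match. The phrase about whether she should continue reaches a woman who is willing to stay, and the protocol-violation entry goes beyond dosing.

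Such missing outcomes are avoidable, because they arise from a decision under the protocol and not from refusal or loss of contact. Each one dilutes the difference, and more so on active treatment, where more women would have responded. If the decisions fall unevenly between arms, the comparison is also distorted.

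**Working it through.** **Inputs.** "Approximately 198 subjects will be randomized in a 2:1 ratio" (synopsis), so 132 on VGX-3100 and 66 on placebo. Planned rates are 35% and 14% with 90% power (Section 2). Phase 2b mITT rates are 39.5% and 15.4% (Section 2.1 of the preceding protocol version; rounded to 40% and 15% in version 3.0). The test is the Miettinen-Nurminen score test at one-sided 0.025. That comes from Section 8.9 of the preceding version and is assumed to carry over, because the version 3.0 text at hand ends in Section 6.1.1.

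**1. The plan's own figure.** Pooled rate = (66 × 0.14 + 132 × 0.35)/198 = 0.28. Null SE = √[0.28 × 0.72 × (1/66 + 1/132)] = 0.0677. Alternative SE = √[0.14 × 0.86/66 + 0.35 × 0.65/132] = 0.0596. Power = Φ[(0.21 − 1.96 × 0.0677)/0.0596] = Φ(1.298) = 90.3%. Exact enumeration of the score test gives 90.8%. The stated 198 subjects and 90% reproduce.

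**2. Losses already in the plan.** Comparing Phase 2b ITT with mITT: 1 − 35/40 = 12.5% on active and 1 − 14/15 = 6.7% on placebo from the rounded rates, or 1 − 35/39.5 = 11.4% and 1 − 14/15.4 = 9.1% from the unrounded mITT rates. Only losses beyond that level cost power.

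**3. Extra loss w (assumed).** A withdrawn woman is taken to have had the mITT chance of response and is now a failure. The rates become 0.35 − 0.395w and 0.14 − 0.154w. Exact power with 132 and 66:

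| w | Both arms: difference | Both arms: power | Active only: difference | Active only: power |
|---|---|---|---|---|
| 0 | 21.0 points | 90.8% | 21.0 points | 90.8% |
| 2% | 20.5 | 89.9% | 20.2 | 88.7% |
| 5% | 19.8 | 88.3% | 19.0 | 85.1% |
| 10% | 18.6 | 85.3% | 17.1 | 77.3% |

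Multiplying the planned rates by (1 − w) and using the normal approximation gives 89.4%, 88.1% and 85.5% for equal loss, and 85.1% and 78.3% for 5% and 10% in the active arm alone. The two methods agree to about one point.

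**4. Unequal loss the other way.** A 10% loss in the placebo arm only would raise the apparent difference to 0.21 + 0.0154 = 22.5 points. With no true effect, 15% response in both arms, and 5% lost on active against 15% on placebo, the observed rates are 0.15 × 0.95 = 14.25% and 0.15 × 0.85 = 12.75%. One-sided rejection is then 4.2% against a nominal 2.5%. With 40% true response in both arms it is 7.6%.

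**5. Can the outcome be recovered?** Not from the withdrawal visit, which yields no tissue. The histology window in the note to Table 7 opens 14 days before Week 36, and tissue taken earlier makes the woman a non-responder in its own right. A late sample could still count, since that note sets no upper limit, but only if she is still being followed.

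**The case against.** The strongest reply is that the protocol leans towards retention. Section 4.3.2 asks that all randomised women be encouraged to complete every visit, and its missed-visit procedure is mostly rescheduling, counselling and tracing. Nothing requires a willing woman to be removed. The planned rates already carry Phase 2b losses, no further rate is given, and an equal extra loss of 2% to 5% costs only about 1 to 3 points of power. Section 4.3.5 considers supplementation if more than 10% discontinue before Week 36. All of this stands and limits the size of the point. It does not remove it. Encouragement sits beside permission to withdraw, and supplementation adds women without recovering lost outcomes.

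A reader might infer more than the text supports:

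- **That women stopped for Grade 4 toxicity lose their Week 36 sample.** Section 4.3.1 keeps them in the study, and Section 2.3 treats cytology, HPV testing, colposcopy and the Week 36 tissue procedure as part of safety monitoring. Only the narrow wording about safety assessment needs tidying.
- **That the sponsor withdraws women.** Its medical monitor is consulted; the site acts.
- **That safety follow-up stops at withdrawal.** Section 4.3.3 has events present at that time followed. Section 7.1.9 of the preceding version keeps pregnant women in safety follow-up unless they are withdrawn.
- **That the two kinds of stopping cannot be separated in the data.** The CRF is not shown, and the preceding version's disposition table reports doses received and completion. What can be said is that 4.3.4 gives one reason list for both.
- **That erythema (78% against 57% in Phase 2b) will make the loss unequal.** No passage links it to missed doses, and Section 2.3 describes these reactions as generally mild and brief.

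**Conclusion.** The point holds as a mismatch between Sections 4.3.2 and 4.3.4 and the non-responder rule in Section 2.1.3 of version 3.0. Following the stated rules can turn an avoidable withdrawal into a recorded treatment failure. It is not a sample-size error, since 198 subjects give 90% power on the stated rates.

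The cost is modest if extra loss is small and balanced (about 90% to 85% power for 2% to 10%). It is larger if the loss is concentrated on active treatment (about 89% to 77%). Imbalance in either direction can bias the test. These figures rest on an assumed withdrawal rate, on withdrawn women having the Phase 2b mITT response rates, and on the one-sided 0.025 score test carrying over. Section 8 of version 3.0 was not available, but no analysis rule can restore samples that were never taken.

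The conclusion does not extend to removing the investigator's discretion over medical or obstetrical complications. That is a clinical matter on which the passages need reconciling.

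**What to change.** - **4.3.2 and 4.3.4:** state that non-compliance, missed visits, an eligibility finding or another protocol violation may end dosing but is not by itself a reason for leaving the study. Such women remain on the visit schedule, with the Week 36 ThinPrep and histology still sought.
- **4.3.4 and the CRF:** record stopping dosing and leaving the study as two items, each with its own reason.
- **4.3.1:** refer to scheduled follow-up assessments, so that the sentence agrees with its own instruction that the woman stay in the study.
- **Medical or obstetrical withdrawal:** reconcile 4.3.1 to 4.3.4 with Section 2.1.3. No clinical rule is proposed here, and when dosing stops is left as written.

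The cost is amendment wording in three subsections and one more CRF item. Sites would follow a few non-adherent women through visits already on the schedule.
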